9.5.1 Institutional level accountability

Management of Study Drug, its ordering, receipt, storage, maintenance, dispensing, destruction and record-keeping will be maintained by the UPMC Investigational Drug Service (UPMC IDS). This will include a complete record of batch numbers and expiration dates of all study treatment, as well as the labels, will be maintained by the UPMC IDS.

9.5.2 Participant Level accountability

A drug dispensing log will be completed for each subject. Subjects will receive all study medication dispensed at the baseline visit and again at the Month 3 post-washout visit. At months 3 and 6, subjects will be instructed to bring all study drug packaging, including unused study drug and empty packaging, to the investigative site. Tablets will be counted for a compliance check and drug accountability. When Study Drug is returned to the site, study staff will return all study drug related materials back to the UPMC IDS for management.

- If the participant misses a dose

If a dose of study drug is missed, the subject should take a dose immediately if on the same day. Otherwise, they can resume normal once daily dosing the following day. The dose should not be doubled to make up for a missed dose within the same day.

9.6 Concomitant Therapies

The following must be avoided during the timeframe in which subjects are taking the study drug therapy.

9.6.1 Off limits

Nitrates or NO donors (such as amyl nitrate) in any form, including topical; phosphodiesterase (PDE) 5 (PDE5) inhibitors (such as sildenafil, tadalafil, vardenafil); and nonspecific PDE inhibitors (theophylline, dipyridamole) are prohibited.

Glucocorticoid maintenance dose increases to higher than 10 mg/day for past 4+ weeks and/or any change or initiation of new DMARDs or biologic agents between study visits will be collected. Subjects with either of these medication changes will be withdrawn. We anticipate the number of subjects requiring RA medication changes to be small, since the inclusion criteria mandates that subjects be on stable doses of RA medications with no anticipated changes over the next 6 months.

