8.2 Exclusion criteria

Subjects who meet any of the following criteria will be excluded from enrollment in the study:

- 1) Aged <18 years old
- 2) Pregnant women
- 3) Known personal history of CVD: clinical diagnoses of
 - a. stroke,
 - b. transient ischemic attack,
 - c. myocardial infarction,
 - d. acute coronary syndrome,
 - e. peripheral arterial disease,
 - f. percutaneous coronary intervention
 - g. coronary bypass graft surgery
- 4) Use of high-dose statins (i.e., atorvastatin 40-80 mg/day or rosuvastatin 20-40 mg/day) currently or within past 3 months, or any dose changes of statins or of blood pressure medications that may affect endothelial function (i.e., angiotensin-converting-enzyme [ACE] inhibitors or angiotensin receptor blockers [ARBs]) within past 3 months. If on statin or an ACE-inhibitor or ARB, there should be no anticipated dose changes over the next 6 months.
- 5) Persons with intra-cardiac and intra-pulmonary shunts, unstable cardiopulmonary conditions, or anyone on chronic oxygen therapy
- 6) Persons taking nitric oxide donors, organic nitrites and nitrates, such as glyceryl trinitrate (nitroglycerin), sodium nitroprusside, amyl nitrite ("poppers")

- 7) Severe hepatic impairment (liver function tests >1.5 times upper limit of normal) within past 4 weeks
- 8) Severe impairment in renal function (serum creatinine \geq 1.5 mg/dL) within past 4 weeks
- 9) Hypotension (defined as blood pressure [BP] <90/60)
- 10) Hereditary degenerative retinal disorders (including genetic disorders of retinal phosphodiesterases)
- 11) Persons already taking (or taken within 3 months) sildenafil or other PDE inhibitors (i.e., tadalafil, vardenafil)
- 12) Persons unable to provide voluntary written informed consent
- 13) Severe hypertension (BP >170/110)
- 14) Persons with HIV/AIDS

8.3 **Justification of selection criteria**

The selection criteria were carefully selected to exclude subjects from the study who may potentially be exposed to specific risks after administering the study drug as well as subjects with conditions that may have an impact on the aims of this study.

Subjects over 65 years old will be excluded due to safety concerns regarding use of the 50 mg daily dose of sildenafil in this age group, and inability to achieve blinding with 25 mg daily dose due to altered pharmacokinetics of the drug if over-encapsulated.

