8.4 Withdrawal of Subjects

Subjects *must* be withdrawn from the study for the following reasons:

- At their own request or at the request of their legally acceptable representative
At any time during the study and without giving reasons, a subject may decline to participate further. The subject will not suffer any disadvantage as a result.
- Development of any of the exclusion criteria except for #4 (new or changed doses of CV and RA medications will be documented and addressed via statistical adjustment).
- If, in the investigator's opinion, continuation of the study would be harmful to the subject's well-being
- Occurrence of AEs or inter-current diseases which the investigator judges unacceptable for continuation of participation in the study
- Pre-specified stopping rules for adverse events: Participants will be automatically withdrawn from the trial if any of the following adverse events occurs: hypotension with BP < 80/50, myocardial infarction, non-arteritic ischemic optic neuropathy, retinal hemorrhage, sudden hearing loss, priapism (prolonged penile erection), and pregnancy.
- Occurrence of adverse drug reactions, which in the investigator's opinion have a negative impact on the subject's individual risk-benefit ratio.
- Non-compliance with the conditions for the trial or instructions by the investigator
- Although not preferred, subjects may interrupt their intake of study medication for reasonable circumstances/reasons at any time (e.g., hospitalization in a remote hospital without study medication access, safety reasons, and side effects). If study medication nonadherence is >50% by pill counts, or if the nonadherence is for 14 or more consecutive days before the study visit, the subject must be withdrawn. In case treatment requires interruption for > 3 days and ≤ 14 consecutive days before the study visit, it is at the discretion of the investigator if the study medication can be restarted. However, any study medication nonadherence will be documented, and interruption of medication use for 3-45 days will be recorded as a protocol deviation.
- In case of pregnancy or breast feeding.

- In case the subject does not tolerate the drug.

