obtained. Blood pressure at each of the four Study Visits #2-5 will be determined using an average of 3 consecutive sitting blood pressure readings. Levels of total cholesterol, low density lipoprotein (LDL), high density lipoprotein (HDL), triglycerides, homocysteine, and lipoprotein (a) will be measured. LDL will be estimated with the Friedewald equation.

Use of statins, ACE-inhibitors, and ARBs including dosages and any dose changes will be recorded. Subjects with any of these medication changes will be recorded as a protocol deviation but will not be withdrawn from the study. We anticipate the number of subjects requiring CV medication changes to be small, since the inclusion criteria mandates that subjects be on stable doses of these CV medications with no anticipated changes over the next 6 months.

11.4 RA Disease-Specific Risk Factors:

The following validated RA disease activity data will be collected at each study visit:

- Routine Assessment of Patient Index Data (RAPID-3) (a modified health assessment questionnaire and patient visual analogue scales)
- DAS28
- CDAI
- RA medication use will be collected at each study visit, including any new medications or dose adjustments made. A complete list of these medications can be found on the RA Medications List CRF. They include
 - DMARDs
 - biologic agents
 - glucocorticoids
 - non-steroidal anti-inflammatory drugs (NSAIDs)
 - Cox-2 inhibitors

Glucocorticoid maintenance dose increases to higher than 10 mg/day for past 4+ weeks and/or any change or initiation of new DMARDs or biologic agents between study visits will be collected. Subjects with either of these medication changes will be recorded as a protocol deviation but will not be

withdrawn from the study. We anticipate the number of subjects requiring RA medication changes to be small, since the inclusion criteria mandates that subjects be on stable doses of RA medications with no anticipated changes over the next 6 months.

RA disease duration from symptom onset will be collected.

11.4.1 Justification of RA Disease-Specific Risk Factors:

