The following validated RA disease activity data will be collected at each study visit: (a) Routine Assessment of Patient Index Data (RAPID-3) (a modified health assessment questionnaire and patient visual analogue scales); (b) DAS28; and (c) CDAI. RA medication use will be collected at each study visit, including any new medications or dose adjustments made. These include DMARDs, biologic agents, glucocorticoids, non-steroidal anti-inflammatory drugs (NSAIDs), and Cox-2 inhibitors. Glucocorticoid maintenance dose increases to higher than 10 mg/day for past 4+ weeks and/or any change or initiation of new DMARDs or biologic agents between study visits will be collected. Subjects with either of these medication changes will be recorded as protocol deviations but will not be withdrawn. We anticipate the number of subjects requiring RA medication changes to be small, since the inclusion criteria mandates that subjects be on stable doses of RA medications with no anticipated changes over the next 6 months. RA disease duration from symptom onset will be collected.

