15.3 POTENTIAL PITFALLS AND SOLUTIONS

15.3.1 How will we account for the potential variability in results of brachial artery FMD measurements?

A number of factors may potentially influence the results of brachial artery FMD. To account for this, subject-specific factors will be minimized by requesting subjects to limit antioxidant vitamin and/or antioxidant-rich diet within 72 hours; document use of CV medications (e.g., β -blockers, calcium channel blockers, NSAIDs, and aspirin); limit tobacco and caffeine use within 12 hours; document the phase of menstrual cycle for premenopausal women (since optimum time for FMD studies is days 1-7 of menses); abstain from exercise within 12 hours; and be fasting and rested before the FMD study. Finally, since we recognize there is diurnal variation in the FMD response, we will attempt to schedule each subject's visits at consistent times of the day.

15.3.2 What if study subject recruitment and retention rates are slower and/or less than anticipated?

We will increase advertising efforts and may open the study at other community rheumatology clinics, with over 6,000 active RA patients. We may include those on statins, ACE-i or ARB (on stable dose x 4+ months), and retain subjects with RA medication changes. We will address these factors statistically, if needed.

15.3.3 How will the effect of comorbidities and RA disease-related factors that affect endothelial function be mitigated so as not to confound the results of sildenafil's effect on endothelial function?

A potential confounder is the effect of traditional CVD risk factors (e.g., DM), CV medications, RA medications, disease activity and duration on potential change in endothelial function over time. As described in Section 4.4, we plan to adjust for these through multivariable linear mixed models. Furthermore, subjects who require a new start or change in RA medication or glucocorticoid maintenance dose increase to 10 mg/day or greater for 4+ weeks during the trial will be withdrawn from the study. Since this is a randomized placebo-controlled study, we anticipate the frequency of these potential confounders will be similar between groups.

15.3.4 Will potential effects of sildenafil risk un-blinding due to altered erectile function or headaches?

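### Sections 9.6.1 and 15.3.3 withdraw participants whose RA drugs change, while 11.4 and 11.4.1 keep them in the trial, and nothing says which rule governs

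*Combined protocol and SAP*

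**What the plan says.** Section 9.6.1 describes two events: a glucocorticoid maintenance dose raised above 10 mg/day for four weeks or more, and any start or change of a DMARD or biologic between visits. It then states: "Subjects with either of these medication changes will be withdrawn".

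Section 11.4 gives almost the same trigger and the opposite consequence: "Subjects with either of these medication changes will be recorded as a protocol deviation but will not be" withdrawn. Section 11.4.1 repeats it: "Subjects with either of these medication changes will be recorded as protocol deviations but will not be withdrawn".

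Section 15.3.3 withdraws "subjects who require a new start or change in RA medication or glucocorticoid maintenance dose increase to 10 mg/day or greater for 4+ weeks".

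Four other places bear on the same participants:

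- **8.4** exempts exclusion criterion 4 from mandatory withdrawal, explaining that "new or changed doses of CV and RA medications will be documented and addressed via statistical adjustment". Criterion 4 in 8.2 does not mention RA drugs. It covers high-dose statins and "any dose changes of statins or of blood pressure medications that may affect endothelial function", specified as ACE inhibitors or ARBs.
- **15.1** includes participants with RA medication changes in the analysis and puts a yes/no change covariate in a secondary sensitivity analysis. Section 15.2 analyses withdrawals by intention-to-treat.
- **15.3.2** lists, among things the team may do if recruitment or retention is poor, to "retain subjects with RA medication changes".
- **15.4** says that, if RA or CV medication changes are numerous, a secondary sensitivity analysis will include those participants.

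For changes in statins, ACE inhibitors or ARBs, 11.3.1 records a deviation and does not withdraw.

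**The concern.** These are operational instructions about removing a person from a trial, and no section gives one precedence over another. Two participants with the same drug change could be handled differently, depending on which page the coordinator consulted.

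The design makes this matter. The primary comparison in 15.1 is within-subject. Someone withdrawn in the first period supplies a baseline and, if 9.7 is applied, one exit reading, but nothing on the second treatment. Section 8.5 rules out replacement. The background sections link inflammation and RA drugs to endothelial function and describe sildenafil as immunomodulatory, so withdrawal for a change in RA therapy could be related to outcome or to treatment. That is a risk; the documents do not show that it would happen.

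Section 15.3.2 adds a further difficulty. If retention is only a fallback, who stays could be decided during the trial. Section 15.4 then blurs the analysis set, because calling inclusion a sensitivity analysis implies exclusion from the primary analysis, contrary to 15.1.

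**Working it through.** **1. The rules side by side**

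| Section | Trigger | Consequence |
|---|---|---|
| 9.6.1 | Glucocorticoid >10 mg/day for 4+ weeks, or DMARD/biologic change or start | Withdraw |
| 11.4, 11.4.1 | Same | Deviation, not withdrawn |
| 15.3.3 | Glucocorticoid ≥10 mg/day for 4+ weeks, or RA medication start or change | Withdraw |
| 8.4 (parenthesis) | New or changed RA or CV drug doses | Document and adjust |
| 15.1 | RA medication change | Included in the analysis |
| 15.3.2 | RA medication change | Retention only as a contingency |
| 15.4 | Many RA or CV changes | Inclusion as a sensitivity analysis |

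The first two rows contradict each other directly. The two dose thresholds differ only for someone raised to exactly 10 mg/day.

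**2. The plan's own power figure**

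Inputs from 15.1 and 15.2: 60 evaluable participants, effect size 0.37, paired t-test, two-sided alpha 0.05. Power comes from the noncentral t distribution with n − 1 degrees of freedom and noncentrality 0.37 × √n. At n = 60 it is 80.5%, so the stated 80% reproduces.

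**3. Room in the recruitment target**

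The synopsis expects about 20% drop-out: 0.20 × 80 = 16, leaving 64. Going from 80 to 60 allows 20 losses (25%), which is 4 more than 16. At n = 64 power is 83.0%.

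**4. Information left after a first-period withdrawal**

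Assume a two-sequence crossover model with period and treatment terms, baseline included, and equal correlation ρ between any two readings on one person. With reading variance σ²:

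- completer: information 1 / [2σ²(1 − ρ)]
- baseline plus one period-1 reading: information 1 / [4σ²(1 − ρ²)]
- ratio: 1 / [2(1 + ρ)]

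The documents do not give ρ. For ρ = 0.3, 0.5 and 0.7 the ratio is 0.385, 0.333 and 0.294, a loss of about 62%, 67% and 71%.

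**5. Effect on power**

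The documents give no rate of RA-drug change, so w, the number of extra withdrawals among 80, is assumed. If these withdrawals already sit inside the 20% drop-out, n stays 64 and power stays 83.0%. If they all come on top of it and all fall in period 1:

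| w | Each contributes nothing: n, power | Each has baseline and exit reading: effective n = 64 − w + w/[2(1 + ρ)], ρ = 0.3 to 0.7 | Power |
|---|---|---|---|
| 2 | 62, 81.8% | 62.8 to 62.6 | about 82% |
| 4 | 60, 80.5% | 61.5 to 61.2 | about 81% |
| 8 | 56, 77.6% | 59.1 to 58.4 | 79-80% |

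**6. Second-period withdrawals**

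Such a participant already has the month-3 reading, and 9.7 calls for the Month 6 procedures, which include FMD and EndoPAT. Both treatments are then measured. If half of the changes fell in period 2 (assumed) and those participants counted as completers, the average loss would be half of 62-71%, about 31-35%. For w = 8 the effective n would be 64 − 4 + 4/[2(1 + ρ)] = 61.5 to 61.2, and power 81.3-81.5%.

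**The case against.** **The intended rule can be inferred.** Section 8.4 is the dedicated withdrawal section and lists no RA-drug change as a reason. Sections 11.4, 11.4.1 and 15.1 agree with it, so 9.6.1 and 15.3.3 may be leftover text. This stands as a guide to the remedy. It does not remove the conflict, because 9.6.1 is an explicit instruction, and 8.4 reaches RA drugs only through a reference to a criterion that does not cover them.

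**The reach of 15.3.3 is uncertain.** A reader might infer that it withdraws anyone who changes an NSAID or Cox-2 inhibitor, since 11.4.1 says of RA medications: "These include DMARDs, biologic agents, glucocorticoids, non-steroidal anti-inflammatory drugs (NSAIDs), and Cox-2 inhibitors". The documents do not settle this. That list also contains glucocorticoids, so importing it whole would make the separate dose threshold in 15.3.3 redundant. Section 9.6.1 itself speaks of RA medication changes when it means the narrower trigger. The wider reach is one possible reading.

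**The loss per withdrawal can be overstated.** A reader might apply the 60-70% figure to every withdrawal. It holds only in period 1. Visits are months apart, so many period-2 changes would probably surface at the final visit, when withdrawal costs little. This objection stands.

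**Few changes are expected.** The protocol says so, and eligibility requires stable RA doses. This also stands and limits the size of the problem.

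**Conclusion.** The contradiction is in current text and should be fixed. Sections 9.6.1 and 11.4/11.4.1 give opposite consequences for one trigger, 15.3.3 sides with withdrawal, and 15.4 does not match 15.1.

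The harm is inconsistent handling of a few participants and, for those withdrawn in period 1, avoidable loss of most of their information. The size of that loss rests on the assumed correlation and on an exit reading being taken.

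Two stronger conclusions might be drawn, and neither is supported. One is that the trial is underpowered. The stated 80% reproduces, no rate of change is given, and these withdrawals may already be within the expected drop-out. Power falls below 80% only when as many as 8 extra withdrawals are assumed, all in period 1. The other is that withdrawal biases the result. The link between RA drugs, inflammation and endothelial function makes outcome-related loss plausible, but nothing in the documents demonstrates it.

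**What to change.** Apply the 11.4/11.4.1 rule throughout.

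- **9.6.1:** replace the withdrawal sentence with: *Either change is a protocol deviation. The participant is not withdrawn for this reason alone, and continues study treatment and visits unless another withdrawal criterion in 8.4 applies.* The qualifier is needed because an unqualified ban on withdrawal would collide with the other mandatory reasons in 8.4, such as the participant's own request, harm, unacceptable adverse events and non-adherence.
- **15.3.3:** remove the withdrawal sentence.
- **15.3.2:** remove the phrase offering retention as a contingency.
- **Trigger:** use one definition everywhere, namely a glucocorticoid maintenance dose above 10 mg/day for four weeks or more, or any DMARD or biologic change or start.
- **8.4:** state that RA-medication changes are not a withdrawal reason, separately from the reference to exclusion criterion 4.
- **15.4:** reword to match 15.1. Participants with RA or CV medication changes are in the primary analysis, and the yes/no time-point covariate is used only in the sensitivity analysis.

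The cost is a sentence or clause in each of five sections, with no new visits or procedures. The downside is that some readings taken after an RA drug change enter the primary model, which is the confounding 15.3.3 set out to avoid. The covariate should stay out of the primary model because it is measured after randomisation and could itself be affected by treatment.

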9.7 Premature Discontinuation of Study Drug

In the event of premature discontinuation of study drug treatment, subjects must undergo the same procedures as outlined for the Month 6 end of study visit.

10. STUDY PROCEDURES

10.1 Timing of procedures

Screening and baseline visits can occur on the same day.

- Visit Windows

There are windows of time specific to any given visit in which the visit may take place without deviating from the protocol by being “Late” or “Early”.

- Baseline Visit must occur within 28 days of Screening, otherwise, Screening must be repeated.
- Three Month Visit must occur three months +/- 7 days after Baseline
- The Two Week Washout Visit must take place between fourteen and seventeen days after Three Month Visit
- Six Month Visit must occur three months +/- 7 days after the Two Week Washout Visit

10.2 Visit Breakdown

10.2.1 Visit 1 – Screening

Screening evaluations will occur after the subject has provided written informed consent. The following evaluations will be performed and information obtained up to 28 days before baseline randomization and the start of study drug treatment:

- Patient information and obtaining of written informed consent
- Eligibility: Assessment of inclusion and exclusion criteria
- Demographic data, including age, gender and ethnicity
- Complete medical history (obtained through patient interview and medical record review)
- Liver function tests and creatinine with GFR. Labs obtained as part of routine clinical care up to 3 months prior to screening will be accepted.
- HIV 1/2 test (results within 3 months prior to screening will be accepted)

If re-screening is required, the liver function tests, creatinine, HIV 1/2 test results, and urine pregnancy test (if applicable) from the previous screening visit may be used if no longer than 3 months prior.

